Bullous dermatitis	Hold study treatment. Grade 1-2 bullous dermatitis: discussion with the Novartis Medical Monitor is required before considering resuming study treatment. Grade 3 bullous dermatitis: consider resuming therapy after expert consultation and documented discussion with the Novartis medical monitor. Grade 4 bullous dermatitis: discontinue study treatment.
Stevens-Johnson syndrome (SJS), or Lyell syndrome/toxic epidermal necrolysis (TEN)	Permanently discontinue study treatment.
Hematology	
Neutropenia (ANC)	
Grade 3 or Grade 4	Hold study treatment. Upon resolution to \leq Grade 2 or baseline within \leq 7 days, resume study treatment without dose modification, after discussion with the Novartis Medical Monitor.
Febrile neutropenia	
Grade 3 or Grade 4	Hold study treatment. Upon resolution of fever and improvement of neutropenia to \leq Grade 2 or baseline, resume study treatment without dose modification, after discussion with the Novartis Medical Monitor.
Thrombocytopenia	

Worst toxicity CTCAE^a grade	Recommended Dose Modification
Grade 3	Hold study treatment. Upon resolution to \leq Grade 2 or baseline, resume study treatment without dose modification. For Grade 3 associated with major bleeding, discontinue study treatment.
Grade 4	Discontinue study treatment.
Anemia	
Grade 3 or Grade 4	Hold study treatment. Upon resolution to \leq Grade 2 or baseline within \leq 7 days, resume study treatment without dose modification.
Lymphopenia	
Any grade	Treatment-related lymphopenia does not require study treatment hold or discontinuation.
Other laboratory adverse events, not specified elsewhere in table and not included in the consensus guidelines	
Grade 3	Hold study treatment. Upon resolution to \leq Grade 1, resume study treatment without dose modification.
Grade 4	Isolated Grade 4 electrolyte abnormalities not associated with clinical sequelae and corrected after appropriate management within 72 hours of their onset do not require discontinuation. In the case of Grade 4 electrolyte imbalances associated with clinical sequelae, or not resolved to \leq Grade 1 within 72 hours despite appropriate management, discontinue study treatment.

Worst toxicity CTCAE^a grade	Recommended Dose Modification
Other non-laboratory adverse events, not specified elsewhere in table and not included in the consensus guidelines	

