Grade 2	Consider study treatment hold, at Investigator discretion. Upon resolution to ≤ Grade 1, resume study treatment without dose modification.
Grade 3	Hold study treatment. Upon resolution to ≤ Grade 1, resuming study treatment must be discussed with the Novartis Medical Monitor.
Grade 4	Discontinue study treatment.

All dose modifications should be based on the worst preceding toxicity.

^a Common Toxicity Criteria for Adverse Events (CTCAE)

*Note: anti-diarrheal medication is recommended at the first sign of abdominal cramping, loose stools or overt diarrhea.

**Note: If Grade 3 or 4 hyper-bilirubinemia is due to the indirect (non-conjugated) component only, and hemolysis as the etiology has been ruled out as per institutional guidelines (e.g., review of peripheral blood smear and haptoglobin determination), then delay study treatment until resolved ≤ Grade 1, and resume study treatment at the discretion of the investigator.

***Note: A CT scan or other imaging study to assess the pancreas, liver, and gallbladder must be performed within one week of the first occurrence of any ≥ Grade 3 of amylase and/or lipase.

[figure not shown]
[figure not shown]

Table 6-3 Criteria for defining dose limiting toxicities for the Japanese safety run-in part

For the purpose of Japanese safety run-in part, DLT defined as follows: Any Grade 4 AEs are DLTs with the exception of:
Neutropenia lasting \leq 5 days that is not associated with fever or other clinical symptoms. Lymphopenia or Leukopenia. Electrolyte abnormalities that are not associated with clinical sequelae or deemed to be not clinically significant and are corrected with appropriate management or supplementation within 72 hours of the onset.
Any Grade 3 AEs are DLTs with the exception of:
Infusion reaction that resolves to \leq Grade 1 within 6 hours. Nausea and vomiting that resolves within 2 days after starting optimal anti-emetic therapy. Thrombocytopenia without significant bleeding. Anemia grade 3 that resolves within 7 days in the absence of transfusion Diarrhea that resolves within 2 days after starting optimal anti-diarrhea treatment. Hypertension that resolves within 7 days after starting treatment. Infection or fever in the absence of neutropenia that resolves within < 5 days. Rash or photosensitivity that resolves within 7 days after starting treatment. Fatigue that resolves within 7 days. Immune-related adverse events that resolve within 7 days after starting treatment with corticosteroids.

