The following Grade 2 AEs are considered DLTs:
Newly emerging total bilirubin \geq 2 x ULN with \geq CTCAE Grade 3 AST/ALT. Pneumonitis that does not resolve within 7 days after starting treatment with corticosteroids. Eye pain or reduction of visual acuity that does not respond to topical therapy and does not improve to Grade 1 severity within 2 weeks of the initiation of topical therapy OR requires systemic treatment. Other clinically significant toxicities, including a single event or multiple occurrences of the same event may be considered as DLTs.

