8.1 Adverse events

8.1.1 Definitions and reporting

An adverse event is defined as the appearance of (or worsening of any pre-existing) undesirable sign(s), symptom(s), or medical condition(s) that occur after patient's signed informed consent has been obtained.

Abnormal laboratory values or test results occurring after informed consent constitute adverse events only if they induce clinical signs or symptoms, are considered clinically significant, require therapy (e.g., hematologic abnormality that requires transfusion or hematological stem cell support), or require changes in study medication(s).

Adverse events that begin or worsen after informed consent should be recorded in the Adverse Events CRF. Conditions that were already present at the time of informed consent should be recorded in the Medical History page of the patient's CRF. Adverse event monitoring should be continued for at least 150 days following the last dose of PDR001 or 30 days after the last dose NIR178, whichever occurs later. After initiation of new post-treatment antineoplastic therapy, only AEs suspected to be related to study treatment will be collected in the Adverse Event CRF. Adverse events (including lab abnormalities that constitute AEs) should be described using a diagnosis whenever possible, rather than individual underlying signs and symptoms. When a clear diagnosis cannot be identified, each sign or symptom should be reported as a separate Adverse Event.

Adverse events will be assessed and graded according to the Common Terminology Criteria for Adverse Events (CTCAE) version 4.03.

If CTCAE grading does not exist for an adverse event, the severity of mild, moderate, severe, and life-threatening, death related to the AE corresponding respectively to Grades 1 - 5, will be used. Information about any deaths (related to an Adverse Event or not) will also be collected through a Death form.

The occurrence of adverse events should be sought by non-directive questioning of the patient (subject) during the screening process after signing informed consent and at each visit during the study. Adverse events also may be detected when they are volunteered by the patient (subject) during the screening process or between visits, or through physical examination, laboratory test, or other assessments. As far as possible, each adverse event should be evaluated to determine:

1. The severity grade (CTCAE Grade 1-5)
2. Its duration (Start and end dates)

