8.1.2 Laboratory test abnormalities

8.1.2.1 Definitions and reporting

Laboratory abnormalities that constitute an Adverse event in their own right (are considered clinically significant, induce clinical signs or symptoms, require concomitant therapy or require changes in study treatment), should be recorded on the Adverse Events CRF. Whenever possible, a diagnosis, rather than a symptom should be provided (e.g. anemia instead of low hemoglobin). Laboratory abnormalities that meet the criteria for Adverse Events should be followed until they have returned to normal or an adequate explanation of the abnormality is found. When an abnormal laboratory or test result corresponds to a sign/symptom of an already reported adverse event, it is not necessary to separately record the lab/test result as an additional event.

Laboratory abnormalities, that do not meet the definition of an adverse event, should not be reported as adverse events. A Grade 3 or 4 event (severe) as per CTCAE does not automatically indicate a SAE unless it meets the definition of serious as defined below and/or as per investigator's discretion. A dose hold or medication for the lab abnormality may be required by the protocol in which case the lab abnormality would still, by definition, be an adverse event and must be reported as such.

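### Table 6-3 spares brief afebrile neutropenia and promptly corrected electrolyte changes from being DLTs at Grade 4 but not at Grade 3, so a milder event can expand the 240 mg Japanese run-in

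*Protocol*

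**What the plan says.** Protocol Table 6-3 (Section 6.2.1) makes every Grade 4 adverse event (AE) in the Japanese run-in a DLT, with three exceptions. The first is neutropenia of 5 days or less without fever or other symptoms. The others are given as "Lymphopenia or Leukopenia. Electrolyte abnormalities that are not associated with clinical sequelae or deemed to be not clinically significant", with the electrolyte exception limited to abnormalities corrected within 72 hours.

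The Grade 3 rule follows: "Any Grade 3 AEs are DLTs with the exception of" ten listed items. Two of these are blood-count events: "Thrombocytopenia without significant bleeding. Anemia grade 3 that resolves within 7 days in the absence of transfusion". Another is an immune-related event that resolves within 7 days of starting corticosteroids. Neutropenia appears in this list only as a condition on the infection-or-fever exception. Leukopenia, lymphopenia and electrolytes do not appear.

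The table closes with a discretionary line: "Other clinically significant toxicities, including a single event or multiple occurrences of the same event may be considered as DLTs".

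Protocol Section 4.1.4 and SAP Section 1.1.4 set the rule at 240 mg plus PDR001. With no DLT in three patients the dose may be declared safe. With one in three, three more patients are enrolled, and the dose may be declared safe if no more than one of six has a DLT. With more than one DLT, the run-in ends and Japanese patients do not join the rest of the study.

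**The concern.** A DLT definition should not be stricter for the milder form of an event than for the severe form. Here a Grade 4 neutropenia that settles in 5 days without fever is ignored, while the same course at Grade 3 counts. The Grade 3 list does exempt thrombocytopenia and anemia under conditions, so blood-count events were evidently not meant to count as a class. The omission looks like a drafting slip.

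Two things are at stake. One is the cohort decision: a toxicity the protocol tolerates at Grade 4 could, at Grade 3, turn a clean cohort of three into an expansion. The other is the reported DLT frequency, which is an endpoint for the run-in (Protocol Table 3-1) and is summarised under SAP Section 2.6.2.6.3.

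**Working it through.** **Step 1. Compare the two lists.**

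| Event | Grade 4 | Grade 3 |
|---|---|---|
| Neutropenia, 5 days or less, no fever or symptoms | exempt | not listed, so a DLT if it is an AE |
| Electrolyte change, no sequelae, corrected within 72 hours | exempt | not listed, so a DLT if it is an AE |
| Lymphopenia or leukopenia | exempt | not listed, so a DLT if it is an AE |

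No other section carries the Grade 4 exceptions down to Grade 3. The closing line of Table 6-3 lets the team add DLTs, not remove them. The SAP has no DLT definition of its own.

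**Step 2. Check whether the Grade 3 events are AEs.** Under Section 8.1.1 a laboratory abnormality is an AE only if it causes signs or symptoms, is clinically significant, needs therapy, or needs a change in study medication.

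- Neutropenia: Table 6-2 requires a hold at Grade 3 or 4 and, after recovery within 7 "days, resume study treatment without dose modification, after discussion with the Novartis Medical Monitor". Section 8.1.2.1 addresses a protocol-required hold or medication: "in which case the lab abnormality would still, by definition, be an adverse event and must be reported as such". Grade 3 neutropenia is therefore an AE.
- Electrolytes: a change that is supplemented needs therapy, so it is an AE. A change that is neither treated nor held for, causes no symptoms and is judged not clinically significant is not an AE, and so not a DLT.
- Lymphopenia: Table 6-2 states "Treatment-related lymphopenia does not require study treatment hold or discontinuation", so it counts only if it is reportable on other grounds. Leukopenia likewise counts only when it is reportable as an AE.
- In every case, an immune-related event that resolves within 7 days of starting corticosteroids is exempt at Grade 3.

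**Step 3. Apply the 240 mg rule.** One such event and no other DLT gives 1/3 instead of 0/3, so three more patients are enrolled. The written rule then ends the run-in only if a further DLT occurs. The chance of at least one DLT in the next three patients is 1 − (1 − p)³: 14.3% at p = 5%, 27.1% at 10% and 48.8% at 20% (assumed rates).

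**Step 4. Illustrate the size.** The plan states no operating characteristics for the run-in, so there is no figure to reproduce. Let b be the per-patient chance of any other DLT in cycle 1 and e the chance of a Grade 3 event of the kinds at issue, assumed independent. Then

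- p = 1 − (1 − b)(1 − e) and q = 1 − p
- P(expansion) = 3pq²
- P(not cleared) = 1 − (q³ + 3pq² × q³)

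Example with b = 0.10, e = 0.04: p = 1 − 0.90 × 0.96 = 0.136 and q = 0.864. Expansion is 3 × 0.136 × 0.864² = 0.305. Not cleared is 1 − (0.645 + 0.305 × 0.645) = 0.159.

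| | e = 0 (after the fix) | e = 1% | e = 2% | e = 4% |
|---|---|---|---|---|
| Expansion, b = 10% | 24.3% | 26.0% | 27.5% | 30.5% |
| Not cleared, b = 5% | 2.7% | 3.7% | 4.8% | 7.5% |
| Not cleared, b = 10% | 9.4% | 10.9% | 12.5% | 15.9% |
| Not cleared, b = 16% | 20.7% | 22.4% | 24.2% | 27.8% |
| Any such event in the first three, 1 − (1 − e)³ | 0% | 3.0% | 5.9% | 11.5% |

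Sources of the rates:

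- b = 5% and 10% are assumed. b = 16% is the 4 DLTs in 25 combination patients of the phase I/Ib study (Protocol Section 1.2.1.4), pooled over 160, 240 and 320 mg. That study need not have used the Table 6-3 definition.
- e is assumed. In the same 25 patients none of these events is among the Grade 3 drug-related AEs seen in at least 5%. Each was therefore seen in at most 1 of 25 (4%). None of the four DLTs was of these kinds.
- Section 2.3 lists the commonest suspected AEs in 165 patients at 160 mg, down to 5.5%, and none of these events is listed.

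The 4% ceiling applies to each event type separately and to drug-related events, whereas Table 6-3 has no causality condition. A higher combined rate is possible but not shown. At b = 10%, assumed values of e of 5%, 10% and 15% give 17.6%, 27.0% and 36.8% not cleared.

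**The case against.** The strongest reply is that the slip has little practical force.

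- **The count is not the whole decision.** Protocol Section 4.2.1 and the note closing SAP Section 1.1.4 rest dose escalation and participation on the whole of the safety data and on what the participating Japanese investigators recommend. This stands. It does not cancel the written expansion and termination rules, but a reader who infers that a single Grade 3 neutropenia would end Japanese participation goes beyond the text. One event expands the cohort; ending the run-in takes a second DLT.
- **Not every such Grade 3 event is a DLT.** This also stands: the steroid-responsive immune-related exception and the AE definition both remove some cases.
- **Earlier cohorts ran without incident.** Three patients were treated at 80 mg and three at 160 mg. One DLT at 80 mg would have ended the run-in, and one in three at 160 mg would have added patients. Neither happened, and Section 4.1.4 says Japanese patients could join other parts. This is fair but weak evidence, because cycle 1 was single-agent NIR178 at lower doses. Even at e = 4%, six patients would all be free of such an event with probability 0.96⁶ = 78%.
- **The size is assumed.** This is correct. The textual inversion does not depend on the rates.
- **The study is closing for lack of efficacy (SAP Section 4).** Correcting the table is therefore unlikely to alter an enrolment decision.

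A reader might also infer that the reported DLT count has been distorted. The documents do not show whether any patient entered the 240 mg run-in cohort, or had such an event.

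**Conclusion.** The inversion is real and Table 6-3 is wrong as written. Brief afebrile neutropenia and promptly corrected electrolyte changes are exempt at Grade 4 and, when they are AEs, count at Grade 3 unless they are steroid-responsive immune-related events. Leukopenia and lymphopenia are affected only when reportable as AEs.

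The point is minor. The error only adds DLTs, so it cannot produce a false declaration of safety. It concerns one planned cohort of 3 to 6 patients and no efficacy endpoint. With other DLTs at an assumed 5% to 16% and these events at an assumed 1% to 4%, the chance of not clearing 240 mg rises by about 1 to 7 percentage points (smallest 2.7% to 3.7%, largest 20.7% to 27.8%). These figures assume independence and mechanical use of the written rule. They illustrate size and are not estimates for this trial.

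**What to change.** Add one sentence to Protocol Table 6-3 stating that the three Grade 4 exceptions (neutropenia, lymphopenia or leukopenia, and electrolyte abnormalities, each under its stated conditions) apply at Grades 3 and 4.

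Check the cycle 1 AEs of any patients treated in the 240 mg run-in cohort, 3 to 6 as planned. If none had such a Grade 3 event, the SAP needs no change. If one did, keep the protocol-defined DLT count as the reported result and add a note giving the count with the event exempted. SAP Section 1 provides the route: an amendment before database lock or an addendum after it.

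The cost is one sentence, a review of at most six planned patients' cycle 1 AEs, and possibly one footnote.

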6.2.2 Follow-up for toxicities

The emergence of Immune-Related AE (irAE) may be anticipated based on the mechanism of action of immunomodulatory therapies.

An irAE is any clinically significant adverse event affecting any organ that is associated with study drug exposure, is consistent with an immune-mediated mechanism, and where alternative explanations have been investigated and ruled out or are considered to be unlikely. Serologic, histologic (tumor sample) and immunological assessments should be performed as deemed appropriate by the Investigator to verify the immune-related nature of the AE. An empiric trial of corticosteroids may also contribute to understanding the etiology of a potential irAE.

Consensus management algorithms for irAEs have been developed and are available to assist investigators in assessing and managing irAEs (refer to [Section 6.2.1](#) Dose modifications).

Patients whose treatment is interrupted or permanently discontinued due to an irAE, AE or clinically significant laboratory value, must be followed-up at least once a week (or more frequently if required by institutional practices, or if clinically indicated) for 4 weeks, and subsequently at approximately 4-week intervals, until resolution or stabilization of the event, whichever comes first.

All patients must be followed up for irAEs, AEs and SAEs for up to 150 days following the last dose of PDR001 or up to 30 days following the last dose of NIR178.

6.2.2.1 Follow up on potential drug-induced liver injury (DILI) cases

Patients with transaminase increase combined with total bilirubin increase may be indicative of potentially severe DILI, and should be considered as clinically important events and assessed appropriately to establish the diagnosis. The required clinical information, as detailed below, should be sought to obtain the medical diagnosis of the most likely cause of the observed laboratory abnormalities.

The threshold for potential DILI may depend on the patient's baseline AST/ALT and total bilirubin value; patients meeting any of the following criteria will require further follow-up as outlined below:

- For patients with normal ALT and AST and total bilirubin value at baseline: AST or ALT > 3.0 x ULN combined with total bilirubin > 2.0 x ULN
- For patients with elevated AST or ALT or total bilirubin value at baseline: [AST or ALT > 3.0 x baseline] OR [ALT or AST > 8.0 x ULN], whichever occurs first, combined with [total bilirubin > 2.0 x baseline AND > 2.0 x ULN]

As DILI is essentially a diagnosis of exclusion, other causes of abnormal liver tests should be considered and their role clarified before DILI is assumed as the cause of liver injury.

A detailed history, including relevant information such as review of ethanol consumption, concomitant medications, herbal remedies, supplement consumption, history of any pre-existing liver conditions or risk factors, should be collected.

Laboratory tests should include ALT, AST, total bilirubin, direct and indirect bilirubin, GGT, GLDH, prothrombin time (PT)/INR, alkaline phosphatase, albumin, and creatine kinase.

Evaluate status of liver metastasis (new or exacerbation) or vascular occlusion – e.g. using CT, MRI, or duplex sonography.

Perform relevant examinations (Ultrasound or MRI, ERCP) as appropriate, to rule out an extrahepatic cause of cholestasis. Cholestasis (is defined as an ALP elevation > 2.0 x ULN with R value < 2 in patients without bone metastasis, or elevation of the liver-specific ALP isoenzyme in patients with bone metastasis).

Note: The R value is calculated by dividing the ALT by the ALP, using multiples of the ULN for both values. It denotes whether the relative pattern of ALT and/or ALP elevation is due to cholestatic ($R \leq 2$), hepatocellular ($R \geq 5$), or mixed ($R > 2$ and < 5) liver injury. For children, there are caveats to calculating the R-ratio as normal levels of ALP are higher than in adults with standard ranges varying by developmental age. In clinical situations where it is suspected that ALP elevations are from an extrahepatic source, the GGT can be used if available. GGT may be less specific than ALP as a marker of cholestatic injury, since GGT can also be elevated by enzyme induction or by ethanol consumption. It is more sensitive than ALP for detecting bile duct injury (<https://livertox.nih.gov/rucam.html>).

Table 6-4 provides guidance on specific clinical and diagnostic assessments which can be performed to rule out possible alternative causes of observed LFT abnormalities.

[figure not shown]
Table 6-4 Clinical and Diagnostic assessments to rule out possible causes of LFT abnormalities

Disease	Assesment
Hepatitis A, B, C, E	
 IgM anti-HAV; HBsAg, IgM & IgG anti-HBc, HBV DNA; anti-HCV, HCV RNA, IgM & IgG anti-HEV, HEV RNA
CMV, HSV, EBV infection	
 IgM & IgG anti-CMV, IgM & IgG anti-HSV; IgM & IgG anti-EBV
Autoimmune hepatitis	
 ANA & ASMA titers, total IgM, IgG, IgE, IgA
Alcoholic hepatitis	
 Ethanol history, GGT, MCV, CD-transferrin
Nonalcoholic steatohepatitis	
 Ultrasound or MRI
Hypoxic/ischemic hepatopathy	
 Medical history: acute or chronic CHF, hypotension, hypoxia, hepatic venous occlusion. Ultrasound or MRI.
Biliary tract disease	
 Ultrasound or MRI, ERCP as appropriate.
Wilson disease (if <40 yrs old)	
 Caeruloplasmin
Hemochromatosis	
 Ferritin, transferrin
Alpha-1-antitrypsin deficiency	
 Alpha-1-antitrypsin

Other causes should also be considered based upon patients’ medical history (hyperthyroidism / thyrotoxic hepatitis – T3, T4, TSH; CVD / ischemic hepatitis – ECG, prior hypotensive episodes; T1D / glycogenic hepatitis).

Obtain PK sample to determine exposure to study treatment and metabolites.

Following appropriate causality assessments, as outlined above, the causality of the treatment is estimated as “probable” i.e. >50% likely, if it appears greater than all other possible causes

of liver injury combined. The term “treatment-induced” indicates *probably caused* by the treatment, not by something else, and only such a case can be considered a DILI case and should be reported as an SAE. All cases confirmed on repeat testing meeting the laboratory criteria defined above, with no other alternative cause for LFT abnormalities identified, should be considered as “medically significant,” and thus, meet the definition of SAE and should be reported as SAE using the term “potential treatment-induced liver injury.” All events should be followed up with the outcome clearly documented

